4.3 Research Protocol

- Control group: Immunosuppressive regimen consisting of calcineurin inhibitor, mycophenolate mofetil, sirolimus or ivermectin
- Lenvatinib group: Participants are given the same anti-rejection therapy as the control group after liver transplantation. 1-2 months after liver transplantation, participants are given lenvatinib with an initial dose of 8 mg (body weight < 60 kg) or 12 mg orally once a day. The initial dose was 8 mg (body weight < 60 kg) or 12 mg orally once a day.
- Delayed administration or reduced dosage may be required if significant clinical toxicity associated with the treatment occurs. If there are some toxicity manifestations and different opinions on treatment, it is recommended to adjust the dose, which can be reduced to the lowest level. All dose adjustments will follow the established dose level.

4.4 Follow up

- Once the treatment is initiated, patients will be regularly monitored for blood and imaging examination. Blood test includes alpha-fetoprotein, alpha-fetoprotein variants, abnormal prothrombin once a month. Imaging examination includes liver ultrasonography once a month, liver MR or CT scanning every 3 months, lung CT every 3 months.
- Multidisciplinary teams determine whether tumors recur based on imaging and serological examinations.
- The follow up duration time is 5 years.
- The primary endpoint is tumor recurrence which refers to the time from treatment to tumor recurrence. Overall survival refers to the time from treatment to death for any reason. The 1, 3, 5-year recurrence-free survival rate and the 1, 3, 5-year overall survival rate will be analyzed.
- The side effects during treatment were recorded. At the same time, patients' status will be scored according to ECOG PS score. Acute or subacute toxicity is classified as level of 0-4, 0 as non-response, 1 as mild, 2 as moderate, 3 as

severe and 4 as life-threatening. The severity of adverse events was judged, reported and handled according to GCP requirements of clinical trials.

5. Safety

Lenvatinib is a clinically approved drug. This study will be conducted in strict accordance with drug specifications and doses.

6. Data analysis and statistical methods

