The Official Title

A Randomized Controlled Study of Lenvatinib Following Liver Transplantation in
Patients with High-Risk Hepatocellular Carcinoma

NCT number: none

Date of the document: November 16, 2019

Hepatocellular carcinoma (HCC) is the third leading cause of cancer deaths worldwide and accounts for about 13,000 deaths in the United States per year [1]. Liver transplantation offers selected patients with localized HCC a chance for cure. For those meeting the Milan criteria, defined as a single tumor 2–5 cm or three or fewer nodules, each 3 cm or less, and no gross vascular invasion, 5 year survival for transplanted patients is about 75% [2, 3]. Meeting these criteria provides additional priority for transplantation in the US. However, for those with HCC beyond the Milan criteria, whether determined pre-transplant or by pathologic evaluation of the explant, the risk of recurrence may be as high as 70% at 2 years after transplantation [4]. There are few studies evaluating adjuvant therapy after resection or transplantation for HCC, and there is no standard of care for the treatment of these patients. Finding an effective agent which decreases recurrence rates in high-risk patients would be a significant advance.

1. Research Purpose

The aim of this study is to observe the efficacy and safety of lenvatinib in preventing high-risk recurrence of hepatocellular carcinoma patients after liver transplantation.

2. Research Protocol

The research is an open, randomized, single-center study. Patients with high-risk recurrence of hepatocellular carcinoma who underwent liver transplantation are included according to the criteria of admission. After operation, the regimen of calcineurin inhibitors, mycophenolate mofetil, sirolimus or everolimus with glucocorticoids removed at an early stage are used. Patients enrolled in the study were randomly allocated in the lenvatinib group (54 patients) and the control group (54 patients) after stable condition. Patients in the control group are given supportive treatment and regular follow-up. Patients in the lenvatinib group are given lenvatinib within 1-2 months after operation (dose: body weight < 60 kg: 8 mg/day, body weight \geq 60 kg 12 mg/day). The baseline data of patients are collected before allocation. Serum and imaging examination are checked regularly every month to monitor the

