recurrence of hepatocellular carcinoma and the side effects of lenvatinib. The efficacy and safety of lenvatinib in patients of high-risk hepatocellular carcinoma are observed, and the clinicopathological factors affecting the efficacy of lenvatinib are analyzed.

When side effects of lenvatinib occur, the dosage can be reduced according to the patients' condition until discontinuation. When tumor recurrence occurs, a multidisciplinary team will draw up specific treatment plans according to the patients'

condition, including surgical resection, interventional therapy, radiofrequency therapy, radiotherapy and targeted therapy (Patients in the control group can add lenvatinib, and patients in the lenvatinib group can decide whether to continue using it according to the patients' condition).

3. Research population

3.1 This study is a single center clinical study. The cases are from patients with hepatocellular carcinoma who underwent liver transplantation in the liver surgery department of Shanghai Renji Hospital.

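### The primary event in this open trial is an unmasked team judgement with no recurrence criteria or dating rule, so calls could come earlier in controls and favour lenvatinib by an amount the documents do not give

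*Combined protocol and SAP*

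**What the plan says.** Section 2 (Research Protocol) sets the design: "The research is an open, randomized, single-center study". No masking of patients, clinicians or assessors is described anywhere.

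Section 4.4 (Follow up) defines the endpoint: "The primary endpoint is tumor recurrence which refers to the time from treatment to tumor recurrence". It says who decides: "Multidisciplinary teams determine whether tumors recur based on imaging and serological examinations".

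The inputs to that decision arrive at different intervals. For serology: "Blood test includes alpha-fetoprotein, alpha-fetoprotein variants, abnormal prothrombin once a month". For imaging: "Imaging examination includes liver ultrasonography once a month, liver MR or CT scanning every 3 months, lung CT every 3 months". The schedule makes no distinction between arms.

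Section 2 also says that a multidisciplinary team plans treatment once recurrence occurs, and describes what then opens up in each arm: "Patients in the control group can add lenvatinib, and patients in the lenvatinib group can decide whether to continue using it".

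The plan does not state what findings constitute recurrence, whether a marker rise alone is enough, whether imaging or pathology must confirm it, or which date is the event date when serology and imaging disagree.

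**The concern.** Three features act together. The primary endpoint is the date of a judgement. The judgement has no stated threshold, and monthly markers and ultrasound leave room to call recurrence now or wait for the next 3-monthly CT or MR. The consequence of the call also differs by arm: it gives controls access to the study drug, whereas patients in the lenvatinib arm already have it.

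If the people making the call know the arm, they have a reason to call early in controls that has no counterpart on lenvatinib. Earlier dating in controls alone would look like delayed recurrence on lenvatinib even if the drug did nothing. Adding lenvatinib after recurrence does not itself change time to recurrence; it matters here only as a reason to make the call.

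**Working it through.** **1. The plan's own sample size.** Inputs from section 6.1: medians 12 and 24 months, 1:1 allocation, 12 months' accrual, 36 months in total, 10% loss. Section 6.2 gives p < 0.05. Two-sided testing and 80% power are assumed, as neither is stated.

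- Hazard ratio under exponential times: 12/24 = 0.50.
- Events (Schoenfeld): 4 × (1.960 + 0.842)² / (ln 0.5)² = 65.3.
- Event probability, with λ = ln 2/median: 1 − [exp(−24λ) − exp(−36λ)]/(12λ). This is 0.820 for controls and 0.577 for lenvatinib, mean 0.699.
- Per group: 65.3/0.699/2 = 46.8, so 47. After 10% loss: 47/0.9 = 52.2, so 53.

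This matches section 6.1, so the point disputes no stated figure. Section 2 gives 54 per group, which is used below; 108 patients yield about 108 × 0.699 = 75 events under the planned effect.

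**2. What arm-dependent dating would do with no true effect.** Simulation: 54 per arm, uniform accrual over 12 months, analysis at month 36, exponential recurrence times with the same median in both arms, detection at the next 3-monthly scan, then a dating shift. A false win is a log-rank z below −1.96 in favour of lenvatinib. The shifts are assumptions.

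| Shift | Median | Hazard ratio | False wins |
|---|---|---|---|
| None | 12 months | 1.00 | about 2.5% |
| Controls 1 month early | 12 months | about 0.89 | about 7% |
| Controls 1 month early | 24 months | about 0.94 | about 5% |

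Repeat runs of the two shifted scenarios gave 0.90 with 7–8%, and 0.93 with 4%, so differences of about a point are simulation noise.

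A second way to set the shift, at a 12-month median, is to move a share of control calls one 3-month scan earlier:

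| Share of control calls moved | Mean shift | Hazard ratio | False wins |
|---|---|---|---|
| 25% | 0.25 × 3 = 0.75 months | 0.95 | 4.5% |
| 50% | 0.50 × 3 = 1.5 months | 0.91 | 8% |
| 100% | 3 months | 0.82 | 17% |

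**3. Adding a delay on lenvatinib.** If half of lenvatinib recurrences are also called one scan late, on top of controls 1 month early, the hazard ratio is about 0.80–0.87 and false wins about 8–17%. This needs a second assumption, taken up under the objection.

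**4. If the planned effect is real.** With 12 versus 24 months and 3-monthly detection, the hazard ratio is 0.52 without a shift. It becomes 0.47 with half of control calls one scan early, and 0.44 if half of lenvatinib calls are also one scan late.

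**The case against.** The strongest reply is that a recurrence call opens several treatments in both arms. Section 2 lists resection, interventional therapy, radiofrequency, radiotherapy and targeted therapy. There is therefore reason to call recurrence promptly in either arm; only access to lenvatinib differs, and section 2 says controls may add it, not that they will. The visit schedule in 4.4 is also common to both arms. This stands, and it limits the likely size of the bias, but the difference in access remains.

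Four stronger readings are tempting, and the documents do not support them:

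- A reader might infer that the plan says the assessing team knows the arm. It does not. Section 4.4 refers to teams that determine recurrence and section 2 to a team that plans treatment, without saying they are the same people. Knowledge of the arm is inferred from the open design and the treatment-planning role. The inference is reasonable but remains an inference.
- A reader might take the larger figures (about 0.80–0.87 and 8–17%) as the expected bias. They need late calls on lenvatinib. The incentive described gives no reason for delay in that arm, only the absence of a reason to hurry.
- A reader might conclude that masked reading would prevent the bias. Unmasked clinicians could still order unscheduled scans more readily in one arm, and a team that also treats the patients may not be maskable.
- A reader might conclude that the planned result is unreliable. If the 12 versus 24 month difference is real, the estimate moves modestly and the conclusion would rarely change.

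**Conclusion.** The concern holds as a possible assessment bias of unknown size. The plan leaves the primary event to judgement in an open trial, without criteria, masking or a dating rule, and a recurrence call has a treatment consequence that differs by arm. The plausible direction favours lenvatinib. The documents do not show that the bias would occur, and no figure in them sizes it.

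On the control-only assumption, which is the one the incentive supports, a 1-month shift with no true effect moves the hazard ratio from 1.00 to about 0.89–0.94 and roughly doubles or triples the false-win rate, from about 2.5% to about 5–7%. The practical risk is that a weak or absent effect is declared a success and the data cannot show otherwise. The figures rest on exponential times, detection at 3-monthly scans, and a shift chosen for illustration. The remedy is inexpensive, so the change should be made.

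**What to change.** Amend section 4.4, for the primary analysis only:

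1. Count recurrence at any site when it is shown on cross-sectional imaging or pathology, dated to the first scan or specimen showing it. A serological rise alone prompts review but is not an event. Any site should be stated, because limiting the event to the scheduled liver and lung scans would drop recurrence imaged elsewhere.
2. Have the radiologists who already report the protocol scans do so without the allocation, and record the event and its date from that report before treatment planning.
3. Analyse the team's unmasked clinical call as a sensitivity analysis. Treatment decisions continue to follow the clinical call, so patient management is unchanged.

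The cost is protocol wording and a small administrative step to keep the arm from the reporting radiologist. Events first suspected on serology would be dated slightly later, in both arms. No extra scan, reader or patient is needed, and the sample size stays at 47, then 53, per group. That the existing radiologists can report without knowing the arm is an assumption the site should confirm. Unscheduled scans ordered by unmasked clinicians would remain a source of bias.

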3.2 Inclusion criteria

- Patients at high risk of recurrence of hepatocellular carcinoma after liver transplantation: extended Milan criteria, without vascular invasion (except for microvascular invasion suggested by pathology after operation)
- Male or female patients aged 18 to 75.
- ECOG physical condition was 0-2 points.
- Child-Pugh A grade of liver function.
- Targeted therapy is acceptable within 1-2 months after liver transplantation. Immunosuppressive regimen consists of calcineurin inhibitor, mycophenolate mofetil and sirolimus.
- No history of surgical resection of liver tumors and targeted drug therapy before liver transplantation.
- Good liver, kidney and bone marrow function: serum albumin > 28g/L, total bilirubin \leq 3 mg/dL (51.3 μ mol/l), ALT and AST \leq 5 times the upper limit of

normal range; serum creatinine \leq 1.5 times the upper limit of normal range; hemoglobin $>$ 90 g/L, neutrophil count (ANC) $>$ 1.5×10^9 /L, platelet count $>$ 60×10^9 /L; PT-INR $<$ 2.3, or PT within 6 seconds over normal upper limit.

- For fertile female patients, the serum/urine pregnancy test should be negative within 7 days before treatment.
- All male and female participants must take reliable contraceptive measures during the trial and within four weeks after the end of the trial.
- The participants have the capability of oral medication.
- The participants must sign the consent form.

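### Both time-to-event endpoints run from treatment, but controls receive no study treatment and randomisation is never named as time zero (minor)

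*Combined protocol and SAP*

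**What the plan says.** Section 4.4 defines recurrence time as follows: "The primary endpoint is tumor recurrence which refers to the time from treatment to tumor recurrence". For survival it says: "Overall survival refers to the time from treatment to death for any reason". It also ties monitoring to a treatment start: "Once the treatment is initiated, patients will be regularly monitored for blood and imaging examination".

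Lenvatinib is the only study treatment with a date, 1–2 months after the operation (Sections 2 and 4.3). For the other arm, Section 2 says: "Patients in the control group are given supportive treatment and regular follow-up". Section 4.3 gives controls the same immunosuppression as the lenvatinib arm, which Section 2 places after the operation.

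On randomisation, Section 2 says: "Patients enrolled in the study were randomly allocated in the lenvatinib group (54 patients) and the control group (54 patients) after stable condition". It gives no date for allocation and no interval from allocation to first dose. It adds: "The baseline data of patients are collected before allocation". Section 4.2 covers only the use of software. Section 6.1 dates the 12-month planning median from transplantation. Section 6.2 names Kaplan–Meier and Cox methods without a time origin.

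**The concern.** The log-rank test, the survival curves and the 1-, 3- and 5-year rates all depend on time zero. The documents offer several candidates: the first lenvatinib dose, the shared immunosuppression after the operation, transplantation itself (the origin of the planning median), and an unstated start near allocation. None is assigned to the control arm.

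If the arms were given different origins, or if pre-dose events were removed from one arm only, the comparison would no longer be the one that was randomised. The trial is open, and Section 6.2 has the researcher check and keep the data before the statisticians receive them. Section 6.1 expects a 10% loss from adjusting the analysis population but gives no rule for it. A written origin is therefore worth having.

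**Working it through.** **Inputs.** From Section 6.1: medians 12 and 24 months, so HR 0.5 under constant hazards; 1:1 allocation; accrual A = 12 months; study time T = 36 months; 10% loss. From Section 2: 54 per arm. From Section 6.2: p < 0.05. Assumed, because not stated: two-sided test, 80% target power, length of the allocation-to-dose gap, shape of the hazard.

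**1. The plan's own figure.** The event probability is P = 1 − [e^(−λ(T−A)) − e^(−λT)]/(λA).
- Control, λ = ln 2/12: 1 − (0.250 − 0.125)/0.693 = 0.820.
- Lenvatinib, λ = ln 2/24: 1 − (0.500 − 0.354)/0.347 = 0.577.
- Schoenfeld events: 4(1.960 + 0.842)²/(ln 0.5)² = 65.3.
- Per arm: 65.3/(0.820 + 0.577) = 46.8, so 47, the plan's figure. (Rounding events up to 66 first gives 48.)
- 47 per arm gives 65.7 events and 80.2% power. 47/0.9 = 52.2, so 53.
- 54 per arm gives 75.4 events and 85.3% power.

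**2. Shared origin.** Simulation at 54 per arm gives HR 0.50 and power 85%; with no true effect the HR is 1.00. There is no bias.

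**3. Recurrences before the first dose.** An undosed patient carries the control hazard, so the expected number is 54 × (1 − 2^(−g/12)), with g in months (30.44 days):

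| Assumed gap | g | Expected of 54 |
|---|---|---|
| 7 days | 0.230 | 0.71 |
| 14 days | 0.460 | 1.42 |
| 28 days | 0.920 | 2.79 |

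These count onsets; fewer would be detected before dosing. The only hint about the gap is in Section 3.2, "the serum/urine pregnancy test should be negative within 7 days before treatment", which applies to fertile women only.

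**4. Controls from randomisation, lenvatinib from first dose, pre-dose events dropped, no true effect.** Simulated, with randomisation assumed at month 1. Cells show HR and one-sided false benefit (nominal 2.5%):

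| Gap | Constant hazard | Weibull shape 0.8 | Weibull shape 0.7 |
|---|---|---|---|
| 7 days | 1.00, 2.6% | 0.99, 2.9% | 0.99, 3.1% |
| 14 days | 1.00, 2.6% | 0.99, 3.0% | 0.97, 3.3% |
| 28 days | 1.00, 2.7% | 0.97, 3.4% | 0.96, 3.9% |

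A steeper assumed fall takes the 28-day figure to about 4.5%. The constant-hazard column differs from 2.5% only by about simulation error.

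**5. Controls from transplantation, lenvatinib from a first dose 1 or 2 months later.** A true HR of 0.50 reads 0.53 or 0.56, and power falls from 85% to about 79% or 70%. With no true effect the HR reads 1.07 or 1.15. The distortion runs against lenvatinib.

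**6. Randomisation as origin, with an undosed gap of 0, 7, 14 or 28 days.** At 54 per arm, power is 85%, 84%, 82% and 80%. At 48 per arm (54 × 0.9 = 48.6), it is 81%, 79%, 78% and 75%.

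**The case against.** A reader might infer that the plan times the two arms differently and that its primary comparison is therefore biased. The documents do not support that. Baseline data precede allocation in both arms, and Sections 3.2, 3.3 and 4.1 speak of the period before treatment for all participants. Both point to a common start, and on that reading there is no bias. Nothing shows that unequal origins are intended.

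A reader might also infer that controls have no datable start at all. That too goes beyond the text, because their immunosuppression is placed after the operation. Transplantation is thus an origin available to both arms, and using it for both would keep them comparable. The difficulty is that several origins are available and none is chosen.

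The count of pre-dose recurrences is fairly called an upper figure. Section 3.3 excludes strongly suspected recurrence, Section 4.1 requires imaging before treatment, and scheduled monitoring begins with treatment. A recurrence arising in a short gap would often be found after dosing and would then have a valid time. The false-benefit figures also need several assumptions together: different origins, one-sided dropping of events, a falling hazard and an unstated gap. All of this stands, and it is why the point is minor.

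What remains is the case that no reading of the current words resolves: a death or detected recurrence before the first dose, or a lenvatinib patient who never starts.

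**Conclusion.** The point holds as a minor defect in the endpoint definitions. Time from treatment is undefined for some randomised lenvatinib patients even on the favourable reading, and the control origin is left to inference.

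On a shared origin the bias is nil. Otherwise the effects are modest and conditional on the assumed gap, hazard shape and data handling. They also differ in direction: dropping pre-dose events under a falling hazard favours lenvatinib, while timing controls from transplantation works against it. Pre-dose deaths and never-starters are not quantified, because the documents give no basis for it.

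**What to change.** In Section 4.4, replace *from treatment* with *from the date of randomisation* in the definitions of both recurrence time and overall survival. State that this applies to every randomised patient, whether or not lenvatinib was started. In Section 6.1, note that the 12-month planning median is dated from transplantation and so does not share that origin.

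The visit schedule need not change. Section 2 describes one regular examination covering "recurrence of hepatocellular carcinoma and the side effects of lenvatinib", and the endpoint can be repaired without splitting it.

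The cost is one phrase in each definition, one sentence in Section 6.1 and a recorded randomisation date. The planned sample size stays as it is. The statistical price is the slight power loss in step 6 of the working. It is about one percentage point at 54 per arm for a 7-day gap and five for 28 days. At 48 per arm with a 28-day gap, power is about 75%, below the 80% that 47 per group implies. That loss comes from the undosed interval itself and is the price of analysing everyone randomised.

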3.4 Exit research

- Participants who have one of the following conditions must stop using drugs immediately and exit the study. At the same time, a comprehensive evaluation will be conducted within 1-2 weeks of the last medication (adverse events, recurrence of tumors, medication for treatment):
- Patients are with poor compliance.
- Prohibited drugs or other drugs that are likely to produce toxicity or result in deviation are used.
- Concurrent diseases or situations that may significantly affect the clinical status and the end point of the study have occurred.
- Clinical signs and laboratory examinations confirm the diagnosis of pregnancy.
- Another malignant tumor has developed.
- The participants are lost to follow-up.
- The participants died.
- Participants or their legal representatives demanded withdrawal from the study

4. Research Progress

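### The plan does not assure adverse-event data from the control arm, and it plans no between-arm safety summary

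*Combined protocol and SAP*

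**What the plan says.** Section 1 sets a double aim: "The aim of this study is to observe the efficacy and safety of lenvatinib". Section 2 describes monthly serum and imaging examinations, whose purpose is to monitor "recurrence of hepatocellular carcinoma and the side effects of lenvatinib". Of the comparison arm it says: "Patients in the control group are given supportive treatment and regular follow-up".

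Section 4.4 holds the routine recording rule: "The side effects during treatment were recorded". The same bullet has ECOG status scored and adds two general sentences: "Acute or subacute toxicity is classified as level of 0-4" and "The severity of adverse events was judged, reported and handled according to GCP requirements of clinical trials". It names no arm, gives no start or stop date for recording, and does not define treatment for a patient who is not on lenvatinib.

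Section 3.4 provides an evaluation that includes adverse events, 1-2 weeks after the last medication, for participants who leave the study. Section 6.2 lists Kaplan-Meier curves and Cox models and no safety analysis. Section 8, on data security and monitoring, is empty.

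**The concern.** Site staff who follow section 4.4 literally have to decide what treatment means for a control patient. Where the protocol discusses toxicity, the word points to lenvatinib: in 4.3, toxicity associated with the treatment leads to a change of dose. A natural outcome is careful recording in lenvatinib patients and little or none in controls.

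The patients are one to two months past a liver transplant, and section 4.3 gives both arms the same anti-rejection therapy. Some events will arise from surgery and immunosuppression whatever the allocation. The randomised control arm is the means of measuring that background. If its events are not collected on the same terms, the safety half of the aim has no concurrent comparator, and the missing data cannot be reliably reconstructed later.

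**Working it through.** The plan gives no safety figure to reproduce. Its only computed figure is the sample size in 6.1 (47 per group; 47/0.9 = 52.2, rounded up to 53), which rests on recurrence and is not affected by this point. The check is therefore mainly of the text.

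**1. What each section settles**

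| Section | In whom | When | How often |
|---|---|---|---|
| 2 (purpose of monitoring) | worded for lenvatinib | not stated | monthly examinations |
| 4.4 (recording side effects) | no arm named | during treatment, undefined | not stated |
| 4.4 (0-4 grade, GCP handling) | general | not stated | not stated |
| 3.4 (exit evaluation) | participants who exit | 1-2 weeks after last medication | once |
| 6.2 (analysis) | no safety analysis | – | – |

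No row, and no combination of rows, states that controls have adverse events recorded on the same schedule and over the same period as lenvatinib patients. The grading and GCP sentences say how events are judged and handled, not in whom or when they are sought.

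**2. After lenvatinib stops.** Section 2 allows dose reduction up to discontinuation for side effects. Stopping for toxicity is not among the exit reasons in 3.4, so it is unclear whether even the single exit evaluation applies to such a patient. Follow-up in 4.4 is 5 years.

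**3. What is lost without controls (assumed rates).** The documents give no event rates, so both cases below are assumptions, with 54 per arm from section 2. Let b be the background risk and d the risk added by lenvatinib. The lenvatinib arm shows b + d, the background share of that is b/(b + d), and the 95% half-width for the risk difference is 1.96 × √[(p1(1 − p1) + p0(1 − p0))/54], with p1 = b + d and p0 = b.

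- b = 30%, d = 20 points: 50% affected; background share 30/50 = 60%; half-width 1.96 × √[(0.25 + 0.21)/54] = 0.181.
- b = 10%, d = 40 points: 50% affected; background share 10/50 = 20%; half-width 1.96 × √[(0.25 + 0.09)/54] = 0.156.

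The lenvatinib arm looks the same in both cases: 27 of 54 affected. Only control data tell an added 20 points from an added 40. With controls, the difference is estimated to within about 16 to 18 points.

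**4. Crossover.** Section 2 lets controls add lenvatinib at recurrence, and 6.1 assumes median times to recurrence of 12 and 24 months. By 12 months, about half of controls (27 of 54) could be eligible. If recurrence times are exponential and deaths and losses are ignored, recurrence by 12 months is 50% against 1 − 0.5^(12/24) = 29%. Mean recurrence-free time in the first 12 months is (1 − 0.5) × 12/ln 2 = 8.7 months in controls and (1 − 0.707) × 24/ln 2 = 10.1 months on lenvatinib. A comparison by arm over the whole period therefore mixes lenvatinib exposure into the controls, while a comparison up to recurrence has unequal time at risk. Both are needed, the second with rates per person-month.

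**The case against.** A reader might infer that the protocol restricts adverse-event recording to lenvatinib patients, so that the control arm will yield nothing. The documents do not support that. The recording sentence names neither drug nor arm, and the toxicity grade and the GCP sentence beside it are general. Section 2 calls control care supportive treatment, and 4.4 uses treatment as the time origin for recurrence and survival, which must cover both arms. The lenvatinib wording in section 2 states a purpose of the monthly examinations and does not limit what is collected.

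A reader might also infer that recording ends with the last lenvatinib dose. Section 3.4 contradicts that as a flat statement, though it offers one evaluation only, and only on exit. The text between the heading of section 7 and 7.2 was not available for this review and could bear on adverse events.

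Finally, the rates in the illustration are assumed. The background share also presumes that every event in the lenvatinib arm would be put down to the drug; the protocol does not say how causality is judged.

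All of this stands, and it changes the conclusion from absent to not assured. It does not supply what is missing: a statement of who is assessed, over what period and how often, and a planned comparison.

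**Conclusion.** The point holds as a gap in specification. Adverse-event collection in controls, and in lenvatinib patients after they stop, is not assured beyond the single exit evaluation, and no between-arm safety summary is planned. If sites read 4.4 by drug exposure, the safety aim is left with an uncontrolled event rate. The size of the resulting misattribution cannot be stated from the documents: it was 20% and 60% of affected lenvatinib patients in two assumed cases, and other rates would give other values. The direction is firmer, since any background risk would be counted with the drug's. The plan should be changed, because the remedy is cheap and data not collected at the time are hard to recover. Nothing here affects the recurrence endpoint or the sample size.

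**What to change.** In 4.4, replace the recording sentence with a rule that all adverse events, whatever their cause, are recorded and graded in both arms at the same monthly visits, from randomisation over one common, stated period, and that recording continues after lenvatinib is stopped. The length of that period has to be written down, since 4.4 gives 5 years of follow-up and 6.1 a study time of 36 months.

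In 6.2, add a safety table by randomised arm: patients affected and event rates per person-month, with the between-arm difference and 95% CI. Because controls may add lenvatinib at recurrence, also report events up to recurrence, or up to the start of lenvatinib in controls, and show later events separately.

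The cost is one protocol paragraph, one table and extra data entry for controls at visits they already attend. No clinical rule changes and no extra patients are needed. The documents give no basis for costing the staff time.
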